7.1 DEMOGRAPHIC AND OTHER BASELINE CHARACTERISTICS

Only descriptive statistics are planned for this section of the report.

7.2 CONCOMITANT DISEASES AND MEDICATION

Only descriptive statistics are planned for this section of the report.

7.3 TREATMENT COMPLIANCE

Only descriptive statistics are planned for this section of the report.

Compliance will be calculated for subjects having attended the visit. A subject is considered having attended the visit if the indicated visit is captured in the eCRF database. In particular, if a subject attended the visit, but is not treated at the visit, the compliance of this visit is considered as 0%.

Compliance with trial medication will be based on the drug infusion/administered eCRF data and calculated as amount of drug infused/administered divided by the amount of drug to be infused/administered expressed as a percentage, see calculations below.

“Per Visit” compliance to trial medication will be calculated as follows:

$$\frac{(\text{Amount of drug infused/administered at Visit X(n)})}{(\text{Amount of drug planned to be infused/administered at Visit X(n)})} \times 100$$

Overall compliance for first treatment cycle of all patients will be calculated as mean of “per visit” compliance at visit Day 1.

Overall compliance for second treatment cycle onwards (from Day 22 onwards) of all patients will be calculated as mean of “per visit” compliance at each visit. Overall compliance to trial medication will be calculated as mean of the “per visit” compliance.

The compliance will be based on the total volume infused in mL (eCRF data) compared to total volume prepared (eCRF data).

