7.7 EXTENT OF EXPOSURE

Treatment exposure will be primarily summarized by the total on-treatment time and has been defined in [Section 5.4](#) of this TSAP.

Treatment interruptions before permanent discontinuation will not be excluded. In Part 1, summary statistics for treatment time by each dose level and the dosage of BI 836880 over time will also be provided.

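### SAP 7.3 gives two denominators for per-visit compliance (amount planned, volume prepared) and averages only over visits captured in the eCRF, so one record can give different compliance figures and infusions missed at visits that did not take place cost nothing

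*SAP*

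**What the plan says.** SAP section 7.3 (Treatment compliance) gives the rule in several steps.

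- **Who counts:** "Compliance will be calculated for subjects having attended the visit". Attendance is a database fact: "A subject is considered having attended the visit if the indicated visit is captured in the eCRF database".
- **Attended but untreated:** "if a subject attended the visit, but is not treated at the visit, the compliance of this visit is considered as 0" (per cent).
- **Ratio in the text:** "amount of drug infused/administered divided by the amount of drug to be infused/administered expressed as a percentage".
- **Denominator in the displayed formula:** "Amount of drug planned to be infused/administered at Visit X(n".
- **Overall figure:** "Overall compliance to trial medication will be calculated as mean of the “per visit” compliance".
- **Closing sentence:** "The compliance will be based on the total volume infused in mL (eCRF data) compared to total volume prepared (eCRF data".

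The section plans descriptive statistics only. Section 6.1 says that patients receive two drugs, BI 836880 and ezabenlimab; section 7.3 does not say whether compliance is calculated for each. Section 7.7 summarises exposure mainly as time on treatment and adds: "Treatment interruptions before permanent discontinuation will not be excluded". For Part 1 it also provides the dosage of BI 836880 over time.

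**The concern.** The amount planned and the volume prepared are different quantities. Infused over prepared shows whether the bag was emptied. It does not show whether the bag held the planned amount. The closing sentence is also the one that names the data fields, so a programmer may well follow it in preference to the formula. Two people working from the same section could then report different figures from the same records.

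The attendance rule is a second, independent problem. The same missed infusion scores 0% if a visit record exists and drops out if none exists. Reported compliance then depends partly on how visits were recorded.

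What is at stake is the reading of a tolerability or activity result at a given dose. A compliance figure that omits infusions not given overstates how much of the scheduled drug was delivered. Time on treatment does not make up for this, because it counts gaps as exposure.

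**Working it through.** The SAP states no compliance figure, so there is nothing to reproduce. The check applies the stated rules to assumed records.

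**Inputs from section 7.3:** two candidate denominators, restriction to visits in the eCRF, 0% for an attended untreated visit, and a simple mean over visits.

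**Assumptions:** 6 scheduled infusions of one drug, 100 units planned at each, 5 given in full and one deviating. The fraction of the volume infused equals the fraction of the prepared drug delivered.

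**Step 1: one visit, two denominators.** The two ratios are linked by

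infused/planned = (infused/prepared) × (prepared/planned).

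They agree only if prepared equals planned. With 50 units prepared and all infused, the volume basis gives 50/50 = 100% and the planned basis gives 50/100 = 50%.

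**Step 2: the mean over six infusions, by type of deviation.**

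| Deviating infusion | Volume prepared, attended visits | Amount planned, attended visits | Amount planned, all scheduled |
|---|---|---|---|
| A. Visit missed, not in eCRF | 500/5 = 100.0% | 500/5 = 100.0% | 500/6 = 83.3% |
| B. Attended, not treated | 500/6 = 83.3% | 500/6 = 83.3% | 500/6 = 83.3% |
| C. Half the planned amount prepared, all infused | 600/6 = 100.0% | 550/6 = 91.7% | 550/6 = 91.7% |
| D. Full amount prepared, half infused | 550/6 = 91.7% | 550/6 = 91.7% | 550/6 = 91.7% |

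(Numerators are sums of per-visit percentages.)

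Row C is where the denominators disagree. Row A is where the attendance rule removes a missed infusion, and it does so under either denominator. Rows B and D show that an infusion withheld at an attended visit, and a full preparation partly infused, lower compliance under every version.

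**Step 3: size of the attendance effect.** If missed infusions count as 0,

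mean over scheduled infusions = mean over attended visits × (attended/scheduled).

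With 8 scheduled infusions, 2 visits not held and the other 6 infusions given in full, the section gives 600/6 = 100%. Over scheduled infusions it is 100% × 6/8 = 75%.

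**The case against.** The best defence is that the formula governs and the closing sentence only names the eCRF fields used to fill it, on the understanding that the prepared volume holds the planned dose. On that reading the two agree unless less than planned is prepared. The reading is reasonable, but the section does not state it, and the case in which the denominators differ is one that a compliance measure should show.

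A second defence is that whether a skipped or delayed cycle still receives a visit record depends on the protocol and the eCRF, which are not at hand. That stands: how often row A occurs cannot be judged. The uneven rule is in the text all the same.

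Third, counting every missed infusion as 0 moves compliance towards dose intensity and mixes withheld doses with non-compliance. This is fair, and is why reporting two figures is an acceptable alternative. It is also true that *planned* needs a definition after a dose reduction, which section 7.8.1 foresees.

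Fourth, other outputs show part of the shortfall: BI 836880 dosage over time in Part 1, and tables of adverse events leading to dose reduction or discontinuation. This also stands. Section 7.7 refers to a definition of on-treatment time in section 5.4, which is not in the text available, so no claim is made that exposure reporting as a whole is deficient.

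A reader might infer three stronger points that the SAP does not support.

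- *An attended untreated visit is both 0% and 0/0.* The explicit 0% rule settles that case, whether or not anything was prepared.
- *Compliance is close to 100% by construction.* Rows B and D lower it, and nothing in the SAP shows how common rows A and C are.
- *Both problems add up, for example 100% against (5 + 0.5)/8 = 68.8% with two missed visits and one half dose.* The 100% requires that the half dose was also prepared at half the amount and that the closing sentence governs. Otherwise the section as written gives 5.5/6 = 91.7%.

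**Conclusion.** The point holds in limited form. Section 7.3 contradicts itself on the denominator, and it treats a missed infusion differently according to whether a visit record exists. The first problem affects only preparations below the planned amount: at such a visit the volume basis exceeds the planned basis by the factor planned/prepared, which is 2 when half is prepared. The second affects only visits absent from the eCRF: 100% against 75% when 2 of 8 are absent and the rest are given in full. These sizes are illustrations on assumed records; the SAP gives no frequencies.

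Severity is minor. The output is descriptive and enters no endpoint, analysis set or decision rule in this SAP. It is still worth correcting, because a stated rule produces a reported number and the text allows more than one value for it.

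**What to change.** In section 7.3:

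1. Keep the planned amount as the single denominator, calculated separately for BI 836880 and ezabenlimab, and state which planned amount applies after a dose reduction.
2. Replace the closing sentence. Use volume infused over volume prepared only to derive the amount delivered when an infusion was incomplete.
3. Count scheduled infusions missed before permanent discontinuation as 0. Alternatively, keep the attended-visit figure and report delivered over planned across all scheduled infusions beside it, with the number of scheduled visits not captured.

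The cost is a short text change and one more derivation, and reported compliance will be lower wherever such visits or preparations occur. The section names only volume fields, so the team should confirm that planned and prepared amounts can be obtained from the collected data. Nothing here concerns the doses themselves.

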7.4 PRIMARY ENDPOINT(S)

The analysis of primary endpoints will be performed as defined in the CTP with the approach proposed by Berry et al. (2013). Posterior distributions for the ORRs will be summarized with Mean, Median, 2.5%, and 97.5 % quantiles.

7.5 SECONDARY ENDPOINT(S)

[figure not shown]
The analysis of secondary endpoints will be performed as defined in the CTP.

7.5.1 Key secondary endpoint(s)

This section is not applicable as no key secondary endpoint has been specified in the protocol.

7.5.2 (Other) Secondary endpoint(s)

Not applicable.

7.7 EXTENT OF EXPOSURE

Treatment exposure will be primarily summarized by the total on-treatment time and has been defined in [Section 5.4](#) of this TSAP.

Treatment interruptions before permanent discontinuation will not be excluded. In Part 1, summary statistics for treatment time by each dose level and the dosage of BI 836880 over time will also be provided.

7.8 SAFETY ANALYSIS

The safety analyses will be performed as defined in the CTP. All safety analyses will be performed on the treated set of Part 1 and Part 2 of this trial.

7.8.1 Adverse events

The analyses of adverse events (AE) will be descriptive in nature. All analyses of AEs will be based on the number of patients with AEs and not on the number of AEs. Two analyses will be performed. The first analysis of safety will be performed for the first part of the trial (determination of the MTD/RP2D, first cycle only, dose level = initial dose at the start of the treatment, treated set). This descriptive analysis will evaluate the MTD/RP2D. The second analysis will be performed with respect to all cycles for part 1 and will act as a support for the determination of the MTD/RP2D (treated set).

For analysis of duration, severity, etc. of multiple AE occurrences, data on the case report form (CRF) will be collapsed into AE episodes provided that all of the following applies:

- The same MedDRA lowest level term was reported for the occurrences.
- The occurrences were time-overlapping or time-adjacent (time-adjacency of two occurrences is given if the second occurrence started on the same day or on the day after the end of the first occurrence).
- Treatment did not change between the onset of the occurrences or treatment changed between the onsets of the occurrences, but no deterioration was observed for the later occurrence.

For further details on summarization of AE data, please refer to the guideline 'Handling and summarization of adverse event data for clinical trial reports and integrated summaries' ([5](#)).

For patients treated with the test drug, that means that all adverse events occurring between first drug infusion and the REP after last drug infusion or death, whichever occurs first, will be assigned to the on-treatment period. All adverse events occurring before any study drug infusion will be assigned to 'screening' and all adverse events occurring after last study drug infusion + the REP will be assigned to 'post-study' (for listings only). For details on the treatment definition, see [Section 6.1](#).

An overall summary of adverse events will be presented. This summary will exclude the rows 'Severe AEs', 'Significant AEs' and 'Other significant AEs' but will include additional rows for 'AEs leading to dose reduction', 'AEs leading to death' and 'AEs by highest Common Terminology Criteria (CTC) grade'.

Additional AE tables will be produced for AEs of special interest (hepatic injury as defined in CTP Section 5.2.7.1 and DLTs as defined in CTP Section 5.2.6.1), providing further details on highest CTC grade, action taken with study drug, and time to first onset of AE.

The frequency of patients with adverse events will be summarized by maximum CTC grade (grades 1, 2, 3, 4, 5 and all grades), treatment, primary system organ class and preferred term for each of the following AE tables as well as relatedness of AEs to treatment and seriousness:

- All AEs

- Drug-related AEs
- Immune-related AEs
- AEs leading to dose reduction
- Drug-related AE leading to dose reduction
- Immune-related AEs leading to dose reduction
- AEs leading to treatment discontinuation
- Drug-related AEs leading to treatment discontinuation
- Immune-related AEs leading to treatment discontinuation
- Drug-related AEs leading to treatment discontinuation or dose reduction
- Immune-related AEs leading to treatment discontinuation or dose reduction
- AEs leading to death
- Serious AEs
- Drug-related serious AEs
- AESIs
- DLTs (in Part 1 dose escalation only)

All tables will be sorted by system organ class (SOC) according to the standard sort order specified by the European Medicines Agency (EMA). Preferred terms (PTs) will be sorted by frequency (within SOC).

The above tables will be repeated with the project-defined grouping of AE terms. Details of the project-defined groupings are defined in the technical TSAP. In these tables, the grouped AEs will replace the original PTs for all AEs that are included within the grouped term. The grouped AE categories will then be tabulated along with all remaining MedDRA PTs, sorted by descending frequency.

A reference table presenting the entire project defined groupings and MedDRA PTs within each grouping will also be produced.

The frequency of patients with user defined AEs will be presented by special search category, preferred term, and highest CTCAE grade. Special search categories (SSCs) for AEs are defined in Table 7.8.1: 1 below.

Table 7.8.1: 1 Definitions of SSCs

N	Medical concept	Definition (for programmers)	Other monitoring options
1	Fatigue / asthenia	HLT 10003550	
2	Hypertension	SMQ 20000147	Narrow
3	Proteinuria	SMQ 20000220	Narrow
4	Haemorrhage	SMQ 20000040 SMQ 20000039	Narrow Narrow
5	Embolic and thrombotic events	SMQ 20000081 SMQ 20000115	Narrow Narrow and broad
6	GI perforation	SMQ 20000107	Narrow

N	Medical concept	Definition (for programmers)	Other monitoring options
7	Infusion related reactions	SMQ 20000021 + PT 10051792 + PT 10082742	Narrow
8	Cardiac failure	SMQ 20000004	Narrow and broad

Additional SSCs for AEs that are to be completed for combination studies with ezabenlimab (BI 754091) are defined in Table 7.8.1: 2 below.

Table 7.8.1: 2 Definitions of SSCs from combination studies with ezabenlimab (BI 754091)

N	Term	Definition#	SMQ code
1	Non-infectious diarrhoea	Noninfectious diarrhea (SMQ) Broad	20000218
2	Drug related hepatic disorders	Drug related hepatic disorders - comprehensive search (SMQ) Broad	20000005
3	ILD	Interstitial lung disease (SMQ) Narrow	20000042
4	Thyroid dysfunction	Thyroid dysfunction (SMQ) Broad	20000159
5	SCAR	Severe cutaneous adverse reactions (SMQ) Broad	20000020
6	Peripheral neuropathy	Peripheral neuropathy (SMQ) Broad	20000034
7	Non-infectious meningitis	Noninfectious meningitis (SMQ) Broad	20000134
8	Non-infectious encephalitis	Noninfectious encephalitis (SMQ) Broad	20000132
9	Acute renal failure	Acute renal failure (SMQ) Broad	20000003
10	Cardiomyopathy	Cardiomyopathy (SMQ) Broad	20000150
11	Guillain-Barre syndrome	Guillain-Barre syndrome (SMQ) Broad	20000131
12	Haematopoietic cytopenias	Haematopoietic cytopenias (SMQ) Broad	20000027
13	Acute pancreatitis	Acute pancreatitis (SMQ) Broad	20000022
14	Cardiac arrhythmias	Cardiac arrhythmias (SMQ) Broad	20000049
15	Heart failure	Cardiac failure (SMQ) Narrow	20000004
16	Vasculitis	Vasculitis (SMQ) Narrow	20000174

This column indicates whether the Term(s) provided in the first column are MedDRA preferred terms (PT), Standardised MedDRA Queries (SMQ), or BI customized MedDRA Queries (BICMQ).

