5.1 PRIMARY ENDPOINT(S)

PART 1:

The primary endpoint is the number of patients with dose limiting toxicities (DLTs) within the MTD evaluation period, which will be assessed for dose escalation in order to determine the maximum tolerated dose (MTD) of the combination of BI 836880 and ezabenlimab.

The MTD is defined as the highest dose with less than 25% risk of the true DLT probability being above 33% and may be considered reached if the probability that the true DLT rate is in the target interval (16%-33%) is sufficiently large during the MTD evaluation period.

The definition of DLTs for solid tumour patients is provided in Section 5.2.6.1 of the CTP.

The MTD evaluation period is defined as the time from the first administration of study treatment to the start of the second treatment cycle, i.e., the first treatment cycle.

PART 2:

The primary endpoint is Objective Response (OR) defined as best overall response (RECIST 1.1) of complete response (CR) or partial response (PR) from first treatment infusion until the earliest of disease progression, death, or last evaluable tumor assessment before start of subsequent anti-cancer therapy, lost to follow-up, or withdrawal of consent. In the case of recurrent glioblastoma (GBM), tumour assessment will be based on RANO (Response Assessment in Neuro-Oncology) criteria.

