6.3 SUBJECT SETS ANALYSED

Screened Set (SCS)

This patient set includes all patients who have signed the informed consent. The screened set will be used for patient disposition tables.

Treated set (TS)

This patient set includes all patients enrolled in the trial who were documented to have received at least one dose of ezabenlimab or BI 836880. The TS is used for both efficacy analysis and safety analyses.

MTD set

[figure not shown]
This patient set includes all patients enrolled in dose escalation and confirmation of MTD cohort of the trial (Part 1) who were documented to have received at least one dose of ezabenlimab or BI 836880 and were evaluable for the MTD determination.

Expansion cohort treated set

This patient set includes all patients enrolled in the expansion part (Part 2) and were documented to have received at least one dose of ezabenlimab or BI 836880.

PK analysis set (PKS)

This patient set includes all patients in the TS who provide at least one evaluable observation for at least one PK endpoint and no PK relevant protocol deviation. PKS is used for statistical PK analysis.

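### The first-cycle MTD/RP2D evaluation and the DLT table are placed on the treated set, while the MTD set defined for evaluable patients has no stated use

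*SAP*

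**What the plan says.** - **SAP Section 5.1.** The Part 1 primary endpoint is the number of patients with a DLT in the first treatment cycle. The MTD is the highest dose at which the risk that the true DLT rate exceeds 33% stays under 25%.
- **SAP Section 6.3.** The MTD set is made up of Part 1 patients who received at least one dose of either drug "and were evaluable for the MTD determination". Uses are stated for the screened set, the treated set (efficacy and safety) and the PK set. None is stated for the MTD set.
- **SAP Section 7.8.1.** The first safety analysis is specified as "determination of the MTD/RP2D, first cycle only, dose level = initial dose at the start of the treatment, treated set", with the purpose: "This descriptive analysis will evaluate the MTD/RP2D". The second, over all cycles of Part 1, is also on the treated set, in a supporting role.
- **SAP Section 7.8.** "All safety analyses will be performed on the treated set of Part 1 and Part 2 of this trial". The list of AE tables in Section 7.8.1 includes "DLTs (in Part 1 dose escalation only"), with no exception to this rule.
- **SAP Section 7.** Unless stated otherwise, percentages are taken over everyone in the patient set, whether or not their value is missing.
- **SAP Section 6.2.** A per protocol analysis of the primary endpoint is allowed as an addition to the treated set, without separating Part 1 from Part 2.
- **SAP Section 7.4.** The primary endpoint analysis is referred to the protocol. The section names no patient set.

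**The concern.** A DLT rate has meaning only among patients observed well enough to say whether a DLT occurred. The SAP recognises this by defining a set that requires evaluability for MTD determination. It then gives the analysis said to evaluate the MTD/RP2D, and the DLT table, to a wider set without that requirement.

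A treated patient who is not evaluable and had no recorded DLT then enters the denominator as a patient without a DLT. Such patients can only lower the percentage, so the reported table makes the dose look better tolerated than the evaluable data show. If the BLRM is run on evaluable patients, as the definition of the MTD set suggests, the report would also carry a DLT table that does not match the counts behind the dose recommendation.

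This is a matter of what the SAP states, not of detail left to the protocol: the set for these tables is named.

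**Working it through.** The SAP gives no DLT count, cohort size or number of non-evaluable patients, so it has no figure to reproduce. The check has three steps.

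**Step 1: which set and denominator apply to the DLT table.**
- The table is one of the AE tables (Section 7.8.1), so it falls under the treated-set rule of Section 7.8.
- Its percentages are over all patients in that set (Section 7).
- The Part 1 treated patients contain the MTD set, because the MTD set adds evaluability to treatment (Section 6.3).

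So the denominator is evaluable plus non-evaluable treated patients at the dose level.

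**Step 2: size of the dilution.** Let x be the number of patients with a DLT, n the evaluable patients and k the treated but non-evaluable patients. Assume the k patients contribute no DLT.

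- MTD set: x / n
- Treated set: x / (n + k)
- Ratio of treated-set to MTD-set rate: n / (n + k), whatever x is

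The counts below are assumed.

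| DLTs / evaluable | MTD set | k = 1 | k = 2 |
|---|---|---|---|
| 1 / 3 | 33.3% | 1/4 = 25.0% | 1/5 = 20.0% |
| 1 / 6 | 16.7% | 1/7 = 14.3% | 1/8 = 12.5% |
| 2 / 6 | 33.3% | 2/7 = 28.6% | 2/8 = 25.0% |
| 2 / 9 | 22.2% | 2/10 = 20.0% | 2/11 = 18.2% |

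With 6 evaluable patients, one extra patient multiplies the rate by 6/7 = 0.857. With k = 0 the two sets coincide and the rate is unchanged.

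**Step 3: would the choice of set matter if the Section 5.1 criterion were applied to these counts?** The BLRM prior is not in the SAP. As a stand-in, take a single-dose Beta(a, b) prior, so that P(rate > 33%) is the upper tail of Beta(a + x, b + N − x) at 0.33, where N is the denominator used.

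| Counts | Uniform prior, Beta(1, 1) | Beta(0.5, 0.5) |
|---|---|---|
| 1/6 → 1/7 | 0.270 → 0.201 | 0.204 → 0.145 |
| 2/9 → 2/10 | 0.307 → 0.241 | 0.255 → 0.195 |

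One added patient can move the value across 0.25. Whether it does depends on the prior: 1/6 is above the limit under the uniform prior and below it under Beta(0.5, 0.5). This step shows only that the set is worth fixing for any model run. It does not describe what the trial's BLRM will do.

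**The case against.** **Treated-set AE tables are normal, and this analysis is called descriptive.** Both are true. The DLT table breaks events down by grade, organ class and preferred term like any other AE table, and general AE tables should stay on the treated set. But the SAP itself gives the descriptive first-cycle analysis the task of evaluating the MTD/RP2D, and it has defined a different set for that purpose.

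**The formal analysis lies elsewhere.** Section 7.4 refers the primary endpoints to the protocol, Section 3 mentions a BLRM, and Section 6.1 leaves escalation decisions to the Safety Monitoring Committee. A reader might infer from Sections 6.2 and 7.8.1 that the BLRM is run on the treated set and that the MTD decision is therefore biased. The SAP does not support that. The Section 6.2 sentence permits an optional per protocol analysis, does not separate the two parts, and may have the Part 2 response endpoint in mind. Nothing states the set for the BLRM, and the name of the MTD set points towards evaluable patients. This objection stands and limits the point to the reported tables.

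**The primary endpoint is a count.** A wider set does not reduce the number of patients with a DLT; only the percentage changes. That is correct. The Section 5.1 criterion, however, concerns the rate, and the tables report percentages.

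**The MTD set may be used somewhere not visible.** The contents list skips several section numbers, and Section 7.8.1 refers to a technical TSAP. The claim is therefore only that no use is stated in the text at hand.

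**Conclusion.** The SAP needs correcting here. The analysis said to evaluate the MTD/RP2D and the DLT table are assigned to the treated set, while the set defined for MTD determination has no stated use.

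The consequence shown is a one-directional dilution of the reported DLT percentage by the factor n / (n + k), and a possible mismatch between that table and a model run on evaluable patients. It rests on two assumptions: that some treated Part 1 patients are not DLT-evaluable, and that they contribute no DLT. The SAP gives neither their number nor the evaluability rule. If there are none, the effect is zero.

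A biased MTD decision is not demonstrated, and the crossings of the 25% limit depend on an assumed prior.

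**What to change.** - In Sections 6.3, 7.8 and 7.8.1, state that the DLT summary and the first-cycle MTD/RP2D evaluation use the MTD set, with evaluable patients per dose level as denominator, and that this is the same set as for the BLRM.
- Keep all other AE tables on the treated set.
- List treated but non-evaluable Part 1 patients by dose level, with the reason for each.
- In Section 6.2, say which set serves the Part 1 primary endpoint.

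The cost is SAP wording and one listing, since the set already exists. DLT percentages may come out slightly less favourable than on the treated set.
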